Seborrheic dermatitis (SD) is a very common skin condition affecting tens of millions of Americans, with over \$300 million spent annually on over-the-counter treatment products (1, 2). Clinically, it is characterized by erythematous, yellowish scaly plaques in the scalp, eyebrows, ears, forehead, nasolabial folds, chest, axillae, and inguinal areas (3). The pathophysiology of SD is not well understood, with three general factors believed to play a role: Malassezia colonization, increased production of lipids by sebaceous glands, and immune abnormalities (4). SD is also more common in men, implicating androgens as a contributing factor. Current clear treatment guidelines are lacking, with some evidence to support topical antifungals (5) and broad-acting topical anti-inflammatory treatments such as steroids and calcineurin inhibitors (6), and non-pharmacological approaches also used (7). That these treatments have been shown to be better than placebo support the contributions of both Malassezia and immune dysregulation in the pathophysiology of the disease. However, as long-term use of steroids is contraindicated, alternative topical approaches are needed and remain under investigation (8, 9). The immune dysregulation underlying SD has not been well characterized, but upregulation of several cytokines and cytokine pathways have been suggested, including Th1, Th2, Th17, (i.e., IL-1 α , IL-1 β , IL-2, IL-4, IL-6, IL-8, IL-10, IL-12, IL-17, TNF- α , and IFN- γ) (10-12). Furthermore, treatment of SD with anti-inflammatory agents such as crisaborole has shown some promise in early studies (9).

TREATMENT RATIONALE:

Current treatments for SD center around topical antifungals, based on the role that Malassezia is believed to play in disease pathogenesis, and anti-inflammatory agents such as topical steroids, which are broad-acting and cannot be applied chronically due to the risk of multiple side effects (11). The pathogenesis of SD is poorly understood, but dysregulated immune markers from different pathways have been suggested, including Th1, Th2, Th17, (i.e., IL-1 α , IL-1 β , IL-2, IL-4, IL-6, IL-8, IL-10, IL-12, IL-17, TNF- α , and IFN- γ).

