- Change from baseline in overall clinical SD score at 4 weeks of treatment with ruxolitinib 1.5% cream applied twice daily

- Change from baseline in each component of the clinical SD score at 4 weeks of treatment with ruxolitinib 1.5% cream applied twice daily (scale, erythema, pruritus)
- Change in overall clinical SD at 6 weeks (i.e., 2 weeks after treatment cessation) from baseline and from 4 weeks
- The frequency, duration, and severity of AEs
- Changes in vital signs
- Changes in laboratory data for hematology, serum chemistry, and urinalysis

Mechanistic (Exploratory) Endpoints

- Determine the molecular cutaneous phenotype of SD at baseline compared with healthy controls, using transcriptomic and proteomic approaches from skin samples acquired by tape-strips
- Identify molecular markers that correlate with disease activity in SD at baseline
- Characterize the change in molecular responses with treatment of topical ruxolitinib 1.5% cream after 4 weeks of treatment
- Identify molecular markers that correlate with treatment response at 4 weeks

STUDY DESIGN OVERVIEW:

This study is an open-label prospective interventional trial. The study will take place at Icahn School of Medicine at Mount Sinai.

The study will include 25 adult patients with moderate-to-severe-SD as well as 20 age- and gender-matched healthy control subjects for comparison. The SD patients will have baseline clinical score of at least 6 using the SD Severity Score in Appendix 1, or an Investigator Global Assessment (IGA) score of at least 3. Enrolled SD subjects will apply topical ruxolitinib 1.5% cream twice daily for 4 weeks. They will return for visits at weeks 2, 4, and 6 following study treatment initiation for repeat clinical assessments, medication reviews, tape-strip, blood and urine sample collections, and monitoring for adverse events.

After providing consent, all subjects will be assessed for study eligibility, which includes a review of the subjects past and current medical conditions, familial medical history and detailed review of past and current medications. SD subjects will also undergo a review of past topical treatments/therapies for SD, and clinical assessments (clinical SD score and IGA).

Subjects who meet inclusion criteria for eligibility may continue with the Baseline Visit (Week 0) or can be scheduled to return for the Baseline Visit within 28 days of the Screening Visit.

SD Subjects:

Seborrheic Dermatitis Ruxolitinib Cream Protocol
Incyte IIR

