- 4) Subject has clinically significant (as determined by the investigator) renal, hepatic, hematologic, intestinal, endocrine, pulmonary, cardiovascular, neurological, psychiatric, immunologic, or other major uncontrolled diseases (e.g., malignancy, TB, HIV, HBV, HCV, thromboembolic events) that will affect the health of the subject during the study, or interfere with the interpretation of study results.
- 5) Subject has previously received treatment with oral or topical JAK inhibitors
- 6) Current other topical treatments (e.g., topical corticosteroids, topical calcineurin inhibitors) within 1 week of baseline
- 7) Use of systemic immunosuppressive medications, including, but not limited to, cyclosporine, systemic or intralesional corticosteroids, mycophenolate mofetil, azathioprine, methotrexate, tacrolimus within 4 weeks of study initiation
- 8) Concurrent use of strong CYP3A4 inhibitors within 7 days or 5 half-lives (whichever is longer). A list of CYP3A4 inhibiting medications can be found in Appendix 3.
- 9) History of adverse systemic or allergic reactions to any component of the study drug.
- 10) Current participation in any other study with an investigational medication
- 11) Subject who is pregnant or breast feeding

Inclusion Criteria For Control Subjects:

- 1) Male or female subjects \geq 18 years of age at the time of signing the informed consent document.
- 2) Subject is able to understand and voluntarily sign an informed consent document prior to participation in any study assessments or procedures.
- 3) Subject does not currently have and does not have a history of SD.
- 4) Female of childbearing potential (FCBP) must have a negative pregnancy test at Screening and Baseline

Exclusion Criteria For Control Subjects:

- 1) Active bacterial, fungal, or viral skin infection within 2 weeks from Screening/Baseline visit.
- 2) Subject has uncontrolled clinically significant (as determined by the investigator) renal, hepatic, hematologic, intestinal, endocrine, pulmonary, cardiovascular, neurological, psychiatric, immunologic, or other disease.
- 3) Subject has previously received treatment with oral or topical JAK inhibitors
- 4) Current other topical treatments (e.g., topical corticosteroids, topical calcineurin inhibitors) within 1 week of baseline

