To the best of our knowledge, this is the first study to evaluate differences in the transcriptome between SD and healthy subjects. A previous study (19) evaluated a fold-change (FCH) of 5 in IL-10 cell counts with coefficient of variation of 50% when comparing 10 SD subjects to 4 healthy volunteers. Assuming similar variability, a sample size of n = 20 SD subjects and n= 20 controls would provide 90% power at 5% significance to detect FCH>2.65 when comparing IL-10 expression between SD and controls, based on a two-sided unpaired t-test applied to log2-transformed RNA-seq data and fold-changes back transformed.

Demographics and Other Baseline Characteristics

Descriptive statistics of demographics and other baseline characteristics of patients will be summarized. Other baseline characteristics include height, weight, vital signs, duration of SD disease, concurrent diagnoses from medical history and indications for concomitant medication, concomitant medication, and previous SD treatments.

Analysis of Primary Endpoint

The one-sided binomial test will be used to verify the hypothesis that the proportion of patients achieving IGA 0/1 at 4 weeks of treatment with ruxolitinib 1.5% cream applied twice daily is greater than 0.4.

Analysis of Secondary Endpoints

The two-sided Wilcoxon signed-rank test will assess the significance of changes from baseline in:

- IGA score at 4 weeks of treatment
- Components of clinical SD scoring (scale, erythema, and pruritus) at 4 weeks of treatment.

The two-sided paired t-test will assess the significance of changes from baseline in:

- Overall clinical SD scoring at 4 and 6 weeks of treatment.
- Vital signs measured in interval or ratio scale
- Analytes measured in interval or ratio scale from laboratory tests (hematology, serum, chemistry, and urinalysis) at 4 weeks of treatment

The p-values will be adjusted by the Bonferroni method. The frequency, duration, and severity of AEs will be summarized with tables and summary statistics.

Analysis of Mechanistic (Exploratory) Endpoints

The baseline immune and molecular cutaneous profile of SD at baseline compared with healthy controls and the change in the immune and molecular cutaneous profile of SD with treatment will be assessed by MMRM approach. Gene/Protein expression data will be modeled using a mixed effect model with the interaction between tissue type (non-lesional/ lesional / healthy) and timepoint as fixed effects and a random effect for each subject.

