RNA-sequencing data will be profiled by Illumina NovaSeq 6000. RNA-sequencing data will be pre-processed using standard quality control metrics, such as FastQC and MultiQC, sequence alignment by STAR RNA-sequencing aligner and sequencing reads assignment to genomic features by featureCounts, followed by *voom*-transform. Mixed effect models will be used on R's limma framework and p-values for the moderated t-tests and paired-t-test will be adjusted by Benjamini-Hochberg procedure. Extensive bioinformatics tools will be employed to gain insights into the results. This will include (but will not be limited to) pathway and gene-set enrichment analyses by R package GSVA (Gene Set Variation Analysis) and by eXploring Genomic Relations (XGR) that uses prior biological knowledge and relationships from public databases.

We will perform proteomic biomarker studies in serum using the OLINK high-throughput proteomic platform, with the Explore panel that evaluates >1,500 protein analytes. Protein expression data will be modeled using a MMRM approach, with the interaction of study group (treatment /control) and timepoint as fixed effects and a random effect for each subject.

We will use the Spearman coefficient to correlate: 1) molecular markers with disease activity in SD at baseline; 2) changes from baseline in molecular markers with changes from baseline in IGA and overall clinical SD scoring at 4 weeks of treatment.

Data Transfer and Management

Data including the patient info, demographics, clinical scores and treatment allocation code will be sent to our Biostatistical Team in password-protected files.

Data from the [name] Lab (where all mechanistic studies will be done), including sequencing data and proteomics will be deposited in the Mount Sinai Box, which has the necessary safeguards for protection of human subjects research.

All data management steps taken to reformat and merge the clinical and laboratory data will be carried out using R codes, so all the steps of the processes can be reproduced.

Management of the Analysis

Analyses will be run in our desktops, with a backed-up copy in the Mount Sinai Box account. Once the analysis is finalized, all data will be deposited into the central file storage system (CFS), which is accessible to all research members. Both Mount Sinai Box and the CFS have backup capabilities and are encrypted and password protected.

Analysis of Safety and Tolerability

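### The controls are described as age- and sex-matched, but no matching rule is given and neither molecular model has an age or sex term for the SD-versus-healthy contrasts

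*Combined protocol and SAP*

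**What the plan says.** The Study Design Overview enrols patients and controls together: "The study will include 25 adult patients with moderate-to-severe-SD", and "20 age- and gender-matched healthy control subjects for comparison". That is the only mention of matching.

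The inclusion criteria for controls set an adult age limit (at least "18 years of age at the time of signing the informed consent document") and a disease-status rule ("Subject does not currently have and does not have a history of SD"). Neither they nor the control exclusions contain an age band, a sex quota or a link to the enrolled patients. The control visit procedures have no matching step.

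Under Analysis of Mechanistic (Exploratory) Endpoints, skin gene and protein expression is modelled with the "interaction between tissue type (non-lesional/ lesional / healthy) and timepoint as fixed effects and a random effect for each subject". Serum proteins are modelled "with the interaction of study group (treatment /control) and timepoint as fixed effects and a random effect for each subject". Neither model lists age, sex or a matched-set term. The power statement for the same comparison uses an unpaired, unadjusted t-test.

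The background section gives the reason why sex matters: "SD is also more common in men, implicating androgens as a contributing factor".

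**The concern.** SD versus healthy is a comparison between different people. The random subject effect handles repeated samples from one person. It cannot remove a difference between the groups in age or sex. If the groups differ on either, a gene or protein that varies with age or sex will show up as a disease marker. Benjamini-Hochberg adjustment limits false discoveries that arise by chance, not those that arise from a systematic shift.

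The second loss occurs even when matching works. Frequency matching balances age and sex between groups, but their variance stays in the error term unless they are modelled. The test is then less sensitive than the data allow.

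At stake is the stated secondary objective of comparing biomarker expression in SD with healthy controls, which is the reason for enrolling the 20 controls.

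**Working it through.** **The plan's own figure.** The plan quantifies nothing about matching. Its one figure for this comparison is a detectable fold change above 2.65 (20 versus 20, two-sided 5%, 90% power, CV 50%, log2 t-test). A CV of 50% gives a log2 SD of sqrt(ln 1.25)/ln 2 = 0.68. The detectable standardised difference is 1.052, so the fold change is 2^(1.052 × 0.68) = 1.64. The 2.65 does not reproduce, but that is a separate matter and nothing below depends on it.

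**Inputs.** From the plan: 25 patients and 20 controls. Assumed, because the documents are silent: no true disease effect, residual SD 1, sex effect 1 SD, and a realised sex imbalance of 20 percentage points.

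**Bias.** Shift in the unadjusted group difference = 0.20 × 1 SD = 0.20 SD. The true standard error, given the sex mix, is sqrt(1/25 + 1/20) = 0.30.

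**Error term.** The unadjusted test also absorbs the within-group variance due to sex. The variance factor is 1 + [m1(1 − m1/25) + m2(1 − m2/20)]/43, where m1 and m2 are the numbers of men.

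- 15/25 versus 8/20: 1 + 10.8/43 = 1.251, estimated SE 0.336
- 20/25 versus 12/20: 1 + 8.8/43 = 1.205, estimated SE 0.329
- 25/25 versus 16/20: 1 + 3.2/43 = 1.074, estimated SE 0.311

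**False-positive rate.** With Φ the standard normal distribution function, the rate is approximately Φ(−(1.96 × SE − 0.20)/0.30) + Φ(−(1.96 × SE + 0.20)/0.30).

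- 15/25 versus 8/20: Φ(−1.53) + Φ(−2.86) = 6.6%
- 20/25 versus 12/20: Φ(−1.48) + Φ(−2.82) = 7.1%
- 25/25 versus 16/20: Φ(−1.37) + Φ(−2.70) = 9.0%

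Simulation of the t-test itself gives about 6.5%, 7% and 8.7%. With age and sex in the model, the shift returns to zero and the rate to about 5%.

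**Sex sampled at random, 70% versus 50% male (no matching at all).** SE = sqrt(1.21/25 + 1.25/20) = 0.333. The rate is Φ(−1.96 + 0.60) + Φ(−1.96 − 0.60) = about 9%.

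**Exact balance, 15/25 versus 12/20 (60% in both).** There is no shift and the variance factor is again 1.251. The rate is 2Φ(−1.96 × sqrt(1.251)) = 2Φ(−2.19) = 2.8%, so the unadjusted test is conservative.

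**Sensitivity (20 versus 20, log2 SD 0.68, assumed sex fold changes of 1.5, 2 and 4).** At 13 versus 9 men, the spurious fold changes are 1.08, 1.15 and 1.32, with rates of about 5 to 7%. At 14 versus 8 men, they are 1.13, 1.23 and 1.52, with rates of 9%, 15% and 24%.

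**Precision.** If age and sex explain R² of the variance, the SE is multiplied by sqrt(1 − R²). This is 0.949 at R² = 0.10 and 0.894 at R² = 0.20, a cut of about 5% and 11%. The equivalent gain in sample size is 1/(1 − R²), or 11% and 25%.

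**The case against.** The design does state matching. If the recruiting team does it well, most of the bias disappears. Three stronger readings are tempting, and the documents support none of them.

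- A reader might infer that sex imbalance is the expected outcome because SD is more common in men. That fact is a reason to match, not evidence that matching will fail.
- A reader might infer that 20 controls cannot be matched to 25 patients. The plan does not promise individual pairs, and frequency matching works at any ratio. The 25 is 20/(1 − 0.20), the dropout allowance, and the mechanistic calculation is 20 versus 20.
- A reader might infer that a 20-point imbalance doubles the false-positive rate to 10%. A 0.20 SD shift set against an uninflated SE does give that figure, but it ignores the variance that the omitted sex effect adds to the error term. At mid-range sex mixes the rate is 6 to 7%.

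It is also fair to say that the endpoint is labelled exploratory, that a raw 5% per marker is not the operating rate after Benjamini-Hochberg adjustment, and that the assumed 10 to 20% of variance is not in the documents. All of this limits the weight of the point. What remains is that the matching has no rule and is not carried into either model, and that adjustment helps whether or not matching succeeds.

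**Conclusion.** The point holds in a limited form: matching is stated, but it is neither specified nor carried into the SD-versus-healthy analysis. Under a 1 SD sex effect and a realised 20-point imbalance, the raw false-positive rate per marker is about 6 to 7% instead of 5%, and about 9% at the extremes. With exact balance it is about 3%, which is lost sensitivity. The sex effect, the imbalance and the share of variance explained are all assumptions.

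Only SD-versus-healthy contrasts are affected. Lesional versus non-lesional skin and baseline versus week 4 are compared within patients, and the primary endpoint does not involve the controls. This is an inexpensive improvement to a secondary objective and exploratory endpoint. It does not show that the disease signatures will be confounded.

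**What to change.** Add age and sex as fixed effects in the limma models and the protein models for every SD-versus-healthy contrast. As additive terms that are constant within a person, they cancel from the within-patient contrasts. One sentence on how controls are matched (for example, frequency matching by sex and age band to the enrolled patients) would complete the change.

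The cost is two degrees of freedom. At 20 versus 20 with balanced groups, the detectable standardised difference moves from 1.052 to 1.054, and power at the former value moves from 90.0% to 89.9%. This gives no credit for reduced residual variance. If the groups are imbalanced there is some further cost: power is 88.5% at a variance inflation of 1.05, 87.0% at 1.10 and 82.5% at 1.25. A 20-point sex imbalance (15/25 versus 8/20) corresponds to about 1.04: the squared correlation of group with sex is 0.04 × 0.2469/0.2499 = 0.0395, and 1/(1 − 0.0395) = 1.04.

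No new visit or sample is needed. Gender is recorded at screening for patients and controls. Age is not named in the visit lists but is known from the 18-year eligibility criterion, and should be entered explicitly in the analysis dataset.

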- 4) Baseline SD score of IGA ≥ 3 with facial involvement
- 5) Subject agrees to discontinue all treatments for SD from screening through study completion aside from the study drug
- 6) Subject has failed an adequate course of treatment with at least one available therapy (topical antifungals or low-potency topical corticosteroids)
- 7) Subject is judged to be in otherwise good overall health as judged by the investigator, based on medical history, physical examination, and laboratory testing. (NOTE: The definition of good health means a subject does not have uncontrolled significant co-morbid conditions).
- 8) Females of childbearing potential (FCBP) must have a negative pregnancy test at Screening and Baseline. While on the study drug and for at least 90 days after the last application of the study drug, male and female participants must be willing to take appropriate contraceptive measures to avoid pregnancy or fathering a child. FCBP who engage in activity in which conception is possible must use one of the approved contraceptive options described below:

Option 1: Any one of the following highly effective contraceptive methods: hormonal contraception (oral, injection, implant, transdermal patch, vaginal ring); intrauterine device (IUD); tubal ligation; or partner's vasectomy.

OR

Option 2: Male or female condom (latex condom or nonlatex condom NOT made out of natural [animal] membrane [for example, polyurethane]); PLUS one additional barrier method: (a) diaphragm with spermicide; (b) cervical cap with spermicide; or (c) contraceptive sponge with spermicide.

The female subject's chosen form of contraception must be effective by the time the female subject is enrolled into the study.

Exclusion Criteria For SD Subjects:

The presence of any of the following will exclude a subject from enrollment:

- 1) SD clinical severity of IGA <3 and SD Severity Score <6 .

Seborrheic Dermatitis Ruxolitinib Cream Protocol
Incyte IIR
March 25, 2022

- 2) Subjects with other skin diseases that would interfere with the study assessment in the opinion of the investigator.
- 3) Active bacterial, fungal, or viral skin infection within 2 weeks from study initiation.

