- 5) Use of systemic immunosuppressive medications, including, but not limited to, cyclosporine, systemic or intralesional corticosteroids, mycophenolate mofetil, azathioprine, methotrexate, tacrolimus within 4 weeks of study initiation
- 6) Current participation in any other study with an investigational medication
- 7) Subject who is pregnant or breast feeding

POTENTIAL RISKS OF RUXOLITINIB 1.5% CREAM:

Based on phase 2 and phase 3 studies in atopic dermatitis, as well as phase 2 studies in vitiligo, topical application of ruxolitinib 1.5% cream shows a good safety profile. The most commonly experienced adverse events in the atopic dermatitis studies were application site burning and pruritus, which occurred more commonly in the vehicle control group (15). These results were mirrored in the phase 2 vitiligo study, with the additional observation of 18% of vitiligo patients experienced development of acne as a treatment-related adverse event (16). Although oral ruxolitinib has been associated with the risk of hematologic abnormalities in patients treated for polycythemia vera or myelofibrosis, pharmacokinetic analysis performed in the phase 3 studies in atopic dermatitis patients with up to 20% body surface area involvement demonstrated plasma ruxolitinib concentrations substantially lower than those required for systemic activity (17).

PRIOR TREATMENT:

All relevant treatment received by the subject within 30 days before screening will be recorded.

PROHIBITED TREATMENT:

Seborrheic Dermatitis Ruxolitinib Cream Protocol
Incyte IIR
March 25, 2022

All treatments prohibited during the screening period are also prohibited throughout the course of the study. All subjects treated previously with a topical or oral JAK inhibitor will be excluded from the study as above.

PROCEDURES:

Monitoring of Aes will begin at the time of signing the informed consent form and will be continued throughout the course of the study. All study procedures will be completed at designated times during the study period (see **Table 1**).

Trained assessors will perform clinical assessments. It is strongly recommended that the same assessor/s perform clinical assessments for a subject at all study visits.

For SD Subjects

Visit 1 – Screening (within 28 days of Baseline)*

- Obtain signed IRB-approved informed consent and HIPPA agreement
- Review Inclusion and Exclusion Criteria
- Record gender, race, ethnicity, and medical history

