The reasons why a subject may discontinue or be withdrawn from the study by the investigator include, but are not limited to the following: subject request, protocol violation, loss to follow up, subject non-compliance, defined as 4 missed applications during the 2 week period between study Visits, study termination by investigators, and a confirmed grade 3 or higher adverse event, which is suspected to be related to study drug administration. Subjects that elect to withdraw from the trial due to lack of efficacy and/or exacerbation of disease will undergo the following: vital signs; blood test; pregnancy test (if applicable); clinical photography; SD clinical assessments; DLQI questionnaire, assessment of concomitant medication and adverse events; blood collection for future mechanistic analysis; lesional tape strip collection.

Stopping Rules

Patients will be permanently discontinued from study treatment in the event of:

- Anaphylactic reaction or other severe systemic reaction to study drug application
- Pregnancy at anytime during the study period
- Diagnosis of a malignancy during study, excluding carcinoma in situ of the cervix, or squamous or basal cell carcinoma of the skin
- Any infection that is opportunistic, whose nature or course may suggest an immuno-compromised status
- Treatment with any prohibited concomitant medication or procedure
- Other reasons that may lead to the permanent discontinuation of study drug include certain Aes deemed related to the study drug.
- If the following lab results are abnormal, participants will be retested in a window of 7-10 days and reassessed. If the test results remain abnormal, participants will be discontinued from the study:

Hematology

Absolute Neutrophil Count: $<1000/\text{mm}^3$; $<1.0 \times 10^9/\text{L}$

Hemoglobin: $<8.0 \text{ g/dL}$; $<4.96 \text{ mmol/L}$; $<80 \text{ g/L}$

Hemoglobin drop $\geq 2 \text{ g/dL}$ from baseline on two consecutive blood draws with associated symptoms; or hemoglobin drop $\geq 3 \text{ g/dL}$ from baseline on two consecutive blood draws without associated symptoms.

Platelet count: $<75,000/\text{mm}^3$; $<75.0 \times 10^9/\text{L}$

Lymphocytes: $<500/\text{mm}^3$; $<0.5 \times 10^9/\text{L}$

Chemistry

AST $>3.0 \times \text{ULN}$

ALT $>3.0 \times \text{ULN}$

Total bilirubin $>1.5 \times \text{ULN}$

CPK $>10 \times \text{ULN}$

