Total bilirubin $\geq 1.5 \times \text{ULN}$; subjects with a history of Gilbert's syndrome may have a direct bilirubin measured and would be eligible for this study provided the direct bilirubin is $\leq \text{ULN}$

- Other intercurrent illnesses or major surgery
- An infection that requires systemic treatment with antibiotic, antifungal, antiviral, anti-parasitic, or anti-protozoal agents or requires oral treatment with such agents for longer than 2 weeks
- Treatment with systemic corticosteroids or non-steroidal immunosuppressive/immunomodulating medications (e.g., cyclosporine, methotrexate, azathioprine, mycophenolate-mofetil, Janus kinase inhibitors, biologic agents, etc.).

Safety Evaluation

Safety and tolerability will be evaluated from the Aes, physical examinations, and vital sign measurements. More frequent safety evaluations may be performed if clinically indicated or at the discretion of the investigator.

Aggregated Aes will be evaluated by the PI/research teams. The local IRB, FDA, and Incyte will be notified of adverse events.

The Principal Investigator (PI) must report all Serious Adverse Events (SAEs) to Incyte within 24 hours of learning of an event, regardless of the PI's causality assessment. This notification should be provided on a completed Serious Adverse Event (SAE) form. SAE reporting for each subject begins the day the informed consent is signed by the patient and within 14 days after subject has completed or discontinued from the study or has taken last dose of the study drug, or as described in the protocol.

SAEs, occurring using Incyte study drug, are reported in accordance with the effective protocol. SAEs occurring with any other commercial drug are reported to the manufacturer of that drug in accordance with regulations and protocol.

Initial SAEs and/or subsequent follow-up reports should be reported via email to [contact] or fax [name]. SAE reports should be for a single subject. SAE forms should be sent with a cover sheet and any additional attachments.

All adverse event information is reported to Incyte on the Principal Investigator's/Institution's Adverse Event Report Form, or a CIOMS-I or MedWatch Form FDA 3500A, or on an Adverse Event Report Form which may be provided by Incyte upon request. The Principal Investigator does not provide medical records (e.g., discharge summary) to Incyte, unless specifically requested.

Reporting of Pregnancy to Incyte

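### The flat 4-week washout in SD exclusion 7 and control exclusion 5 leaves a long-acting biologic stopped just over 4 weeks earlier admissible, a probably small risk to the exploratory molecular comparisons

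*Combined protocol and SAP*

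**What the plan says.** Exclusion Criteria For SD Subjects, item 7, bars "Use of systemic immunosuppressive medications, including, but not limited to, cyclosporine, systemic or intralesional corticosteroids, mycophenolate mofetil, azathioprine, methotrexate, tacrolimus within 4 weeks", counted back from the start of the study. Exclusion Criteria For Control Subjects, item 5, has the same wording and the same window. Any previous JAK inhibitor is excluded without a time limit (SD item 5, control item 3). No other drug criterion sets a washout for a biologic.

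Two neighbouring rules are drafted differently:

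- The Stopping Rules list "Treatment with systemic corticosteroids or non-steroidal immunosuppressive/immunomodulating medications (e.g., cyclosporine, methotrexate, azathioprine, mycophenolate-mofetil, Janus kinase inhibitors, biologic agents, etc", but under the lead-in "Patients will be permanently discontinued from study treatment in the event of". They govern treatment during the study and set no look-back before entry.
- SD exclusion 8 uses a half-life window: "Concurrent use of strong CYP3A4 inhibitors within 7 days or 5 half-lives (whichever is longer").

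On medication history, the Study Design Overview calls for a "detailed review of past and current medications", with no time limit and no exclusion attached. Prior Treatment and the screening visits require drugs to be recorded for 30 days before screening. For SD patients, prior SD therapies are recorded without a time limit (Visit 1; Table 1, footnote 2). Past medical conditions and history of inflammatory skin disease are recorded for both groups (Table 1, footnote 1).

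The molecular comparisons stand under "Mechanistic (Exploratory) Endpoints".

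**The concern.** The Stopping Rules treat biologic and immunomodulating agents as disqualifying once a patient is on study, but entry has no washout matched to how long such agents last. The list opens with "Use of systemic immunosuppressive medications, including, but not limited to, cyclosporine", so it can be read to cover an immunosuppressive biologic, but only within 4 weeks. A long-acting one stopped on day 29 before entry passes. A lesser gap is a current drug judged immunomodulating but not immunosuppressive.

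What is at stake is the molecular work: SD versus healthy at baseline, and the change from Week 0 to Week 4. For a transcript raised in SD, a suppressed control widens the apparent difference and a suppressed SD patient narrows it. The random subject effect in the planned mixed model absorbs a stable within-patient shift. It does not remove a shift between SD and healthy subjects, or a carry-over that fades between Week 0 and Week 4. Fading carry-over would be expected to work against the cream, so that bias is conservative.

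**Working it through.** **1. What other rules catch**

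| Rule | What it acts on | Does it close the gap? |
|---|---|---|
| SD inclusion 7 | Good overall health, investigator judgement | In part; about disease, not residual drug |
| SD exclusion 2: "Subjects with other skin diseases that would interfere with the study assessment in the opinion of the investigator" | Other skin disease | In part, SD patients only |
| SD exclusion 4 | Significant systemic disease, including immunologic, that affects health or interpretation | In part, SD patients only |
| Control exclusion 2 | Uncontrolled disease only | No, if the disease is well controlled |
| Control inclusion 3 | Present or past SD | No |
| Prohibited Treatment | Carries forward what screening already prohibits | No |
| Stopping Rules | Study treatment | No; controls receive none |

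**2. Residual drug (half-lives are assumptions; the documents give none)**

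Fraction remaining = 0.5^(days / half-life). Day 29 is the first admissible day; day 57 = 29 + 28 is Week 4. The last column is the longer of 28 days and 5 half-lives.

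| Half-life (days) | Day 29 | Day 57 | Washout under the proposed rule (days) |
|---|---|---|---|
| 3 | 0.1% | <0.1% | 28 |
| 4 | 0.7% | <0.1% | 28 |
| 7 | 5.7% | 0.4% | 35 |
| 14 | 24% | 6% | 70 |
| 21 | 38% | 15% | 105 |
| 28 | 49% | 24% | 140 |

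For half-lives of 7 days or shorter the flat window is adequate or nearly so. At 5 half-lives, 0.5^5 = 3% remains. Residual drug level is not the same as residual effect on skin transcripts.

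**3. Recording window for drugs not taken for SD**

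Thirty days before screening, plus 0 to 28 days from screening to baseline, gives 30 to 58 days before baseline. That falls short of the 70 to 140 days in the last three rows.

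**4. Size of the effect on a single transcript**

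Inputs from Sample Size Calculation, Mechanistic Endpoint: 20 v 20, two-sided unpaired t-test on log2 data, 5% significance, 90% power, 2.65-fold.

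- The standardised difference giving 90% power is 1.052. Since log2(2.65) = 1.406, the implied standard deviation is 1.406 / 1.052 = 1.34 log2 units.
- Simulation with normal log2 data and this standard deviation, with k of 20 subjects shifted down, returns the planned 90% power and 5.0% false-positive rate when k = 0.

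| Assumed scenario | k = 1 | k = 3 |
|---|---|---|
| SD patients lose the whole 2.65-fold difference: power | about 86% | about 76% |
| Controls suppressed 2-fold, no true difference: false-positive rate | about 5.0% | about 6% |

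Moving the mean alone gives 86.9% and 78.7% for the first row. The simulated figures are lower because a mixed group is also more variable. All figures are for one nominal test, before Benjamini-Hochberg adjustment.

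**The case against.** The strongest case against is that this is a preference rather than an error. The 5-half-life window in SD exclusion 8 addresses a drug interaction and sets no standard for molecular washout. A rule for stopping treatment need not mirror an entry look-back. The documents describe SD therapy as topical or non-pharmacological, so a patient recently on a biologic most likely took it for another disease, which brings SD exclusions 2 and 4 into play. Controls are called healthy in the Study Design Overview. Past conditions are on record for both groups, so many relevant histories would surface. Nothing in the documents suggests that several such subjects would enter.

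Most of this stands, and it sets the size of the point. It does not close the gap: the safeguards turn on disease and judgement rather than residual drug, and for controls they reach only uncontrolled disease.

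A reader might infer three stronger things that the documents do not support:

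- *Biologics in current use are admissible.* The open-ended list already covers an immunosuppressive biologic within 4 weeks, and any earlier JAK inhibitor is barred.
- *Nothing before the 30-day recording window would be known.* That limit does not apply to prior SD therapies or to past medical conditions.
- *Power could fall much further.* An assumed 4-fold suppression in 3 of 20 SD patients gives 67%. But 4-fold is 2 log2 units against a modelled difference of 1.41, so it places patients who must enter with IGA of at least 3 about 1.5-fold below healthy skin. Complete loss of the difference is already an extreme case.

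**Conclusion.** The gap is real on the text: no drug criterion bars a subject who stopped a long-acting biologic just over 4 weeks earlier. The consequence is probably small and confined to the exploratory molecular comparisons. One affected subject in 20 costs about 4 points of power at worst, or leaves the false-positive rate at about 5.0%. Three in 20 would cost about 14 points, or raise the rate to about 6%. These figures rest on assumed numbers of subjects, suppression and half-lives, none of which the documents give.

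A reader might extend the point to the primary IGA 0/1 test. The documents do not support that: SD patients must have active disease at entry despite any carry-over, and fading carry-over would be expected to work against the cream. This is a cheap improvement, not a flaw that threatens the trial.

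**What to change.** In SD exclusion 7 and control exclusion 5, add immunomodulating medications, including biologic agents, within 4 weeks or 5 half-lives, whichever is longer. In the medication-history item for both groups, record such drugs over that same window for any indication. The final drug list is for the investigator.

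The cost is wording in two criteria and one history item. The downside is that a few candidates with recent biologic use become ineligible. If eligibility is left as it is, the longer recording alone would still allow a sensitivity analysis without the exposed subjects; an exposure never recorded cannot be handled later.
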